For each phase of study, results will be summarized by dose level and regimen. Tabulations will be produced for appropriate demographic and baseline clinical characteristics, efficacy, pharmacokinetic, and safety parameters. For categorical variables, summary tabulations of the number and percentage of patients within each category of the parameter will be presented. For continuous variables, the number of patients, mean, median, standard deviation, minimum, and maximum values will be presented. Time-to-event data will be summarized using Kaplan-Meier methodology using 25th, 50th (median), and 75th percentiles with associated 2-sided 95% confidence intervals. Graphical displays will be presented, as appropriate. Results will be evaluated for all patients.

TABLE OF CONTENTS

INVESTIGATOR'S SIGNATURE PAGE.....	2
ALRN-6924-1-01 SYNOPSIS.....	3
TABLE OF CONTENTS.....	21
LIST OF TABLES.....	25
LIST OF FIGURES	25
ACRONYM LIST.....	26
1 BACKGROUND AND STUDY RATIONALE	29
1.1 Therapeutic Rationale for Inhibiting MDM2/MDMX to Restore p53 Activity	29
1.2 Stapled Peptide Technology	30
1.3 ALRN-6924.....	30
1.4 Nonclinical Experience with ALRN-6924	30
1.4.1 Pharmacology.....	30
1.4.2 Toxicology and Nonclinical Safety.....	31
1.4.3 Pharmacokinetics and Absorption, Distribution, Metabolism and Excretion	33
1.4.4 ALRN-6924 Administered in Combination with Palbociclib	34
1.5 Clinical Experience with ALRN-6924	41
1.6 Clinical Experience with Palbociclib	41
2 STUDY OBJECTIVES	42
2.1 Phase 1 Dose Escalation (ALRN-6924 administered as single agent therapy)	42
2.1.1 Primary Objectives.....	42
2.1.2 Secondary Objectives	42
2.1.3 Exploratory Objectives.....	42
2.2 Phase 2a Dose Expansion (ALRN-6924 administered as single agent therapy)	42
2.2.1 Primary Objectives.....	42
2.2.2 Secondary Objectives	42
2.2.3 Exploratory Objectives.....	43
2.3 Phase 2a Dose Expansion in MDM2 Amplified or MDM2/CDK4 Co-amplified Solid Tumors (ALRN-6924 plus palbociclib)	43
2.3.1 Primary Objectives.....	43
2.3.2 Secondary Objectives	43
2.3.3 Exploratory Objective	43
3 INVESTIGATIONAL PLAN	44

3.1	Study Rationale	44
3.2	Study Overview.....	44
3.2.1	Pharmacokinetic, Pharmacodynamic, and Clinical Activity Assessments.....	47
3.3	Number of Patients and Centers.....	49
3.4	Duration of Study	49
4	PATIENT POPULATION	50
4.1	Inclusion Criteria – Phase 1 dose escalation (ALRN-6924 administered as single agent therapy)	50

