5.3 Study Drug Administration

The investigational agent ALRN-6924 as well as palbociclib (IBRANCE®) will be provided by Aileron and distributed to clinical sites. Patients should begin treatment with study drug within 21 days following the start of clinical screening. Issues that would cause treatment delays should be discussed with Sponsor's Medical Monitor.

Treatment of patients in the dose escalation and the dose expansion phases of the study will continue until unacceptable toxicity, patient or physician decision to discontinue therapy, or disease progression that is either symptomatic, rapidly progressive, requires urgent intervention, or is associated with a decline in performance status. Patients receiving clinical benefit despite evidence of suspected or confirmed PD may continue on study after a discussion between the Principle Investigator and Medical Monitor.

ALRN-6924 will be administered by IV infusion in D5W. The pre-defined dose will be calculated for each patient based on body weight at the start of each cycle. During the first two cycles, ALRN-6924 should be administered in the morning to allow observation of delayed infusion reactions.

Phase 1 Dose Escalation:

Treatment Regimen	Infusion Days	Infusion Time	Additional notes
DR-A	1, 8, 15 of a 28-day cycle	1 hour (± 15 min)	At the end of the infusion, IV fluids (saline) or oral fluids (500 mL – 1000 mL) should be administered, unless clinically contraindicated.
DR-A-2	1, 8, 15 of a 28-day cycle	2 hours (± 15 min)	At the end of the infusion, IV fluids (saline) or oral fluids (500 mL – 1000 mL) should be administered, unless clinically contraindicated. Administer dexamethasone (4 mg orally or IV) approximately 4 hours after the end of the infusion in Cycles 1 and 2, and thereafter at the discretion of the investigator.
DR-B	1, 4, 8, 11 of a 21-day cycle	1 hour (± 15 min)	At the end of the infusion, IV fluids (saline) or oral fluids (500 mL – 1000 mL) should be administered, unless clinically contraindicated.

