3.4 Evaluation of Best Overall Response

The best overall response is the best response recorded from the start of the treatment until disease progression/recurrence (taking as reference for progressive disease the smallest measurements recorded since the treatment started). The patient's best overall response assignment will depend on findings of both target and non-target disease and will also take into consideration the appearance of new lesions. Furthermore, depending on the nature of the study, it may also require confirmatory measurement. Specifically, in non-randomized trials where response is the primary endpoint, confirmation of PR or CR is needed to deem either one the "best overall response."

It is assumed that at each protocol-specified time point, a response assessment occurs. The following table provides a summary of the overall response status calculation at each time point for patients who have measurable disease at baseline.

Time point response: Patients with target (\pm non-target) disease

Target Lesions	Non-target Lesions	New Lesions	Overall Response
CR	CR	No	CR
CR	Non-CR / non-PD	No	PR
CR	Not evaluated	No	PR
PR	Non-PD or not all evaluated	No	PR
SD	Non-PD or not all evaluated	No	SD
Not all evaluated	Non-PD	No	NE
PD	Any	Yes or No	PD
Any	PD	Yes or No	PD
Any	Any	Yes	PD
CR=complete response, PR=partial response, SD=stable disease			
PD=progressive disease, NE=inevaluatable			

Complete or partial responses may be claimed only if the criteria for each are confirmed by a repeat assessment at least 4 weeks later. In this circumstance, the best overall response can be interpreted as shown in the following table:

Best overall response when confirmation of CR and PR required

Overall response First time point	Overall response Subsequent time point	BEST overall response
CR	CR	CR
CR	PR	SD, PD or PR*
CR	SD	SD provided minimum criteria for SD duration met, otherwise PD
CR	PD	SD provided minimum criteria for SD duration met, otherwise PD
CR	NE	SD provided minimum criteria for SD duration met, otherwise NE
PR	CR	PR
PR	PR	PR
PR	SD	SD
PR	PD	SD provided minimum criteria for SD duration met, otherwise PD
PR	NE	SD provided minimum criteria for SD duration met, otherwise NE
NE	NE	NE
CR=complete response; PR=partial response; SD=stable disease; PD=progressive disease; NE=inevaluable		

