4.2. CLINICAL ACTIVITY ENDPOINTS

- Overall response - objective evidence of complete response (CR) or partial response (PR). The evaluation of overall response will be based on response, as determined by the investigator, in accordance with RECIST version 1.1, for subjects with solid tumors, or IWG 2014 criteria, for subjects with lymphomas.

- Overall Response Rate (ORR) - proportion of subjects with overall response
- Time to Response (TTR) - time from the date of the first dose of ALRN-6924 to the date of the first documentation of overall response. The TTR will be calculated as follows (in months):

$$(\text{date of first response (CR/PR)} - \text{first dose date} + 1)/30$$

Subjects who do not respond will be censored at their last tumor assessment.

- Duration of Response (DOR) - time from the first documentation of overall response to the first documentation of objective or clinical disease progression or death due to any cause. This endpoint is only assessed among subjects who achieve overall response at some point during the study. The DOR will be calculated as follows (in months):

$$(\text{date of disease progression/death} - \text{date of first response (either CR or PR)} + 1)/30$$

Version V.1

Subjects who do not have disease progression (or death) will be censored at the last known time point that the subject was progression-free. Subjects with two or more consecutive missing response assessments prior to a visit with progression (or death) will be censored at the last date of tumor assessment when the subject was known to be progression free.

- Disease control - objective evidence of CR, PR, or stable disease (SD). The evaluation of disease control will be based on response, as determined by the investigator, in accordance with RECIST version 1.1, for subjects with solid tumors, and IWG 2014 criteria, for subjects with lymphomas.
 - Disease Control Rate (DCR) - proportion of subjects with objective evidence of disease control
 - Duration of Clinical Benefit (DCB) - time from the first documentation of disease control to the first documentation of objective or clinical disease progression or death due to any cause. This endpoint is only assessed among subjects who achieve disease control at some point during the study. The DCB will be calculated as follows (in months):

(date of disease progression/death - date of first response (either CR/PR/SD) + 1)/30

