5.2. EFFICACY EVALUABLE POPULATION

The Efficacy Evaluable Population is defined as those subjects who meet all of the following criteria:

- Received at least one dose of ALRN-6924 at a dose level at least 0.8 mg/kg per infusion.
- Have at least one post-baseline evaluation or had clinical disease progression
- Are TP53 wild type or indeterminate (as assessed by the central lab; if not assessed by central laboratory, as assessed by the local laboratory)

This population will be used for analyses of clinical activity.

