9. CLINICAL ACTIVITY ANALYSES

ORR and DCR will be summarized by frequency counts, percentages, and the two-sided 95% CIs. The Wilson score method will be used to construct the confidence intervals.

The distribution of TTR and PFS will be summarized using Kaplan-Meier methodology grouped. The 25th, 50th (median), and 75th percentiles will be provided, along with their two-sided 95% CIs.

The distribution of DOR (among responders) and DCB (among subjects experiencing clinical benefit) will be summarized using Kaplan-Meier methodology grouped. The 25th, 50th (median), and 75th percentiles will be provided, along with their two-sided 95% CIs.

The best overall response (BOR) will be summarized by frequency counts and percentages of subjects achieving each possible category (complete response, partial response, stable disease, progressive disease).

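### Time to response (TTR) in the Phase 1 SAP: Kaplan-Meier percentiles that censor non-responders who died, or whose response window closed at progression, can show a percentile the observed response proportion never reaches (minor)

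*SAP*

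**What the plan says.** SAP Section 4.2 defines TTR as running from first dose to first documented complete or partial response, so response is the only event. The censoring rule is "Subjects who do not respond will be censored at their last tumor assessment". Section 9 states "The distribution of TTR and PFS will be summarized using Kaplan-Meier methodology grouped", and asks for the 25th, 50th and 75th percentiles with 95% confidence intervals. Section 5.2 names the analysis set, the Efficacy Evaluable Population: "This population will be used for analyses of clinical activity". That set expressly admits subjects with clinical progression.

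Duration of response (DOR) is treated differently. Section 4.2 says of it: "This endpoint is only assessed among subjects who achieve overall response at some point during the study". Section 9 repeats the restriction for DOR and attaches none to TTR.

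Two parts of the protocol bear on when a response can still count. Appendix K, Section 3.4, says for solid tumors: "The best overall response is the best response recorded from the start of the treatment until disease progression/recurrence". Section 5.3 says: "Patients receiving clinical benefit despite evidence of suspected or confirmed PD may continue on study". The SAP's own best overall response (BOR, Section 4.2) is the highest response level recorded, with no cut-off at progression. For lymphomas, neither document says whether progression closes the response window.

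On format, the Statistical Methods part of the protocol synopsis says: "Time-to-event data will be summarized using Kaplan-Meier methodology using 25th, 50th (median), and 75th percentiles". Neither document mentions competing risks or cumulative incidence.

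**The concern.** Kaplan-Meier censoring assumes that a censored subject would go on to have the event at the same rate as those still under observation. That is reasonable for a subject who is alive, progression-free and simply not followed further. It cannot hold for a subject who has died. It also fails for a solid-tumor subject whose best-response window has closed under Appendix K. For response, these are competing events.

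Treating them as censoring shrinks the risk set without lowering the attainable response proportion, so one minus Kaplan-Meier (1-KM) exceeds the proportion who actually respond. The report could then print a quartile of TTR beside an overall response rate (ORR) below that quartile. A reader could take the quartile to mean that a quarter or half of the subjects had responded by that time. SAP Section 3.1 asks for tables by dose cohort, and Protocol Section 3.2 describes cohorts of 3 to 6, so a single late response can move the curve a long way.

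**Working it through.** The documents give no TTR figure, response rate or progression rate, so there is no stated number to reproduce. The check has three parts.

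**1. Worked cohorts (no assumed rates)**

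Inputs: first scans at weeks 8 and 16 (Protocol Section 6.10: before Cycle 3, then every other 28-day cycle, for the once-weekly regimens), and the SAP formula for TTR in months, (response date − first dose date + 1)/30.

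*Distorted case, n = 6.* Three solid-tumor subjects progress at week 8, and one of the remaining three responds at week 16.

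| Scan | At risk | Responses | Censored under the SAP rule | 1-KM | Cumulative incidence |
|---|---|---|---|---|---|
| Week 8 | 6 | 0 | 3 | 0% | 0% |
| Week 16 | 3 | 1 | – | 1 − 2/3 = 33.3% | 1/6 = 16.7% |

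The 25th percentile is printed as (112 + 1)/30 = 3.8 months. ORR is 1/6 = 16.7%, so a quarter of the cohort never responded.

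*Undistorted case, n = 6.* Two subjects respond at week 8. Then 1-KM = 2/6 = 33.3% before anyone is censored, ORR is at least 33.3%, and the 25th percentile of (56 + 1)/30 = 1.9 months is correct.

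*Lower limit on cohort size.* One responder gives ORR = 1/3 = 33.3% at n = 3 and 1/4 = 25% at n = 4. A 25th percentile printed with ORR below 25% is therefore impossible in cohorts of 3 or 4, and first possible at n = 5 (1/5 = 20%).

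**2. Size of the overstatement (rates assumed)**

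Let r be the per-scan probability of response and q that of progression or death, constant over k scans, with progression treated as closing the window.

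- 1-KM after k scans = 1 − (1 − r)^k
- Cumulative incidence = r[1 − (1 − r − q)^k]/(r + q)

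Take k = 6 (weeks 8 to 48, before imaging may become less frequent after one year):

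| r, q (assumed) | 1-KM | Cumulative incidence |
|---|---|---|
| 0.03, 0.60 | 1 − 0.97^6 = 16.7% | 0.03(1 − 0.37^6)/0.63 = 4.7% |
| 0.05, 0.50 | 1 − 0.95^6 = 26.5% | 0.05(1 − 0.45^6)/0.55 = 9.0% |
| 0.10, 0.30 | 1 − 0.90^6 = 46.9% | 0.10(1 − 0.60^6)/0.40 = 23.8% |

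These are three illustrations, not a range over all plausible rates.

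**3. How often the mismatch would show in a cohort of six**

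Simulating the same three scenarios (400,000 cohorts each, six scans), a 25th percentile is printed while ORR is below 25% in about 8%, 14% and 18% of cohorts. In the third scenario a 25th percentile is printed in 61% of cohorts. In about 44% of all cohorts it is printed with ORR at or above 25%, so there most printed 25th percentiles do not contradict the ORR.

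**The case against.** The strongest reply is that the SAP does what the protocol asks. The synopsis prescribes Kaplan-Meier percentiles for time-to-event data without excepting TTR, and Protocol Section 7.1 says the analyses are descriptive. No test, sample size or decision rule is broken. Escalation rests on dose-limiting toxicity and safety review. ORR with Wilson intervals and BOR stand beside TTR, and Section 3.1 promises listings of all data, so with few responders a reader could see each response date. All of this stands, and it limits the severity. It does not remove the point: the protocol names a format but sets no population or competing-event rule for TTR, and the percentile itself can mislead.

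A second reply concerns progression, and it stands in part. Treatment may continue past progression, and the SAP's BOR has no progression cut-off. The closed window comes only from Appendix K, which the SAP reaches through its reference to RECIST 1.1. Death is therefore the only undisputed competing event. Progression is one for solid tumors if Appendix K governs. For lymphomas the documents do not say.

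A reader might also infer that every TTR percentile will be either not estimable or driven by subjects leaving the risk set. The undisturbed cohort above shows otherwise. Nor does the mismatch with ORR threaten all cohorts of 3 to 6, since for the 25th percentile it cannot occur at 3 or 4.

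**Conclusion.** The concern holds as a minor point. As written, the TTR rule treats death as ordinary censoring, and for solid tumors under Appendix K it does the same with progression. 1-KM then overstates the cumulative incidence of response, and a percentile can be printed that the observed response proportion never reaches. The cohort of six (3.8 months beside 16.7%) shows this without any assumed rate, but it does rely on progression closing the window. If only death counts, the same arithmetic applies to subjects who die.

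The three scenario figures (16.7% against 4.7%, 26.5% against 9.0%, 46.9% against 23.8%) rest on assumed constant rates that merge progression with death and allow no response after progression. Other pairs give different answers, so they should not be read as bounds.

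Two wider inferences are not supported. ORR and BOR are simple counts and are unaffected. The point also does not carry over to Phase 2a, where response is a primary objective, because SAP Section 3.1 assigns that phase a separate analysis plan.

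**What to change.** Either of two changes to SAP Sections 4.2 and 9 would do.

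- **Simpler:** summarise TTR among responders only (n, median, range), printed next to ORR. This borrows the restriction already used for DOR, not its Kaplan-Meier format.
- **Alternative:** report the cumulative incidence of response with death as a competing event, and progression too wherever it closes the response window. Censor at the last tumor assessment only subjects with none of these events.

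In either case, reconcile the SAP definition of BOR with Appendix K on whether a response after progression counts for solid tumors, and state the rule for lymphomas. Record the departure from the synopsis's Kaplan-Meier format in SAP Section 11.

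The cost is SAP wording and programming. Progression and death dates are already needed for progression-free survival, so no new data are collected. The drawback of the responder-only summary is that it is conditional on responding and rests on few subjects, so it must be read together with ORR.

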APPENDIX K: RECIST 1.1 – Assessment of Clinical Activity for Patients with Solid Tumors

Although response is not the primary endpoint of this study, patients with measurable disease will be assessed at baseline and during the study by standard criteria. Patients should be reevaluated after receiving 2 cycles of study therapy and then after every 2 cycles thereafter. In the event objective response (PR or CR) is noted, changes in tumor measurements must be confirmed by repeat assessments that should be performed at least 4 weeks after the criteria for response are first met. For stable disease (SD), follow-up measurements must meet the SD criteria at least 5 weeks after study entry.

1. Definitions

Response and progression will be evaluated in this study using the international criteria (version 1.1) proposed by the Response Evaluation Criteria in Solid Tumors (RECIST) Committee [Eur J Cancer. 45 (2009) 228-247]. Changes in only the largest diameter (unidimensional measurement) of the tumor lesions are used in RECIST 1.1. Note: Lesions are either measurable or non-measurable using the criteria provided below. The term “evaluable” in reference to measurability will not be used because it does not provide additional meaning or accuracy.

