2. STUDY DESIGN

2.1. BRIEF DESCRIPTION

This is a Phase 1/2a open-label, multi-center, dose-escalation study designed to evaluate the safety, tolerability, PK, PD, and antitumor effects of ALRN-6924 in subjects with advanced solid tumors or lymphomas with WT TP53.

The Phase 1 portion of the study, referred to as the dose escalation phase (DEP), is a “3+3” dose escalation design to establish the MTD and OBD of ALRN-6924. Dose cohorts are delineated in the study protocol.

Two regimens are explored in the Phase 1 portion of the study:

- Dose Regimen A: once weekly for 3 consecutive weeks (Days 1, 8, and 15 of a 28-day cycle)
- Dose Regimen B: twice weekly for 2 consecutive weeks (Days 1, 4, 8, and 11 of a 21-day cycle)

The Phase 2a portion of the study, referred to as the dose expansion phase (EXP), will enroll up to 5 distinct groups of subjects with specific solid tumors and/or lymphomas to further investigate the clinical safety profile and potential efficacy of ALRN-6924 at the MTD or OBD. A third dosing regimen, Dose Regimen C, will also be explored during the EXP. Subjects assigned to this regimen will receive ALRN-6924 on days 1, 3, and 5 of a 21-day cycle.

Treatment of subjects in the dose escalation and the dose expansion phases of the study will continue until documentation of disease progression, unacceptable toxicity, or subject or physician decision to discontinue therapy. Subjects receiving clinical benefit may continue on study after a discussion between the Principle Investigator and Medical Monitor.

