Subjects who do not have disease progression (or death) will be censored at the last known time point that the subject was progression-free. Subjects with two or more consecutive missing response assessments prior to a visit with progression (or death) will be censored at the last date of tumor assessment when the subject was known to be progression free.

- Best Overall Response (BOR) - the highest level of objective response recorded (complete response, partial response, stable disease, or progressive disease) for each subject
- Progression-free Survival (PFS), defined as the time from the date of the first dose of ALRN-6924 to the date of first evidence of objective or clinical disease progression or the date of death, due to any cause, whichever occurs first. The PFS will be calculated as follows (in months):

(date of disease progression/death - first dose date + 1)/30

Subjects who do not have disease progression (or death) will be censored at the last known time point that the subject was progression-free. Subjects with two or more consecutive missing response assessments prior to a visit with progression (or death) will be censored at the last date of tumor assessment when the subject was known to be progression free.

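### For Phase 1 solid tumors, the SAP's best overall response omits Appendix K's confirmation rule and stop at progression, so BOR can be overstated and ORR, TTR and DOR are left exposed

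*SAP*

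**What the plan says.** **SAP 4.2 (Clinical Activity Endpoints).** BOR is "the highest level of objective response recorded (complete response, partial response, stable disease, or progressive disease) for each subject". No confirmation, minimum duration of stable disease, cut-off at progression or not-evaluable category is given. ORR and DCR have their own definitions and are not built on BOR. A responder is a subject with objective evidence of CR or PR, and disease control adds SD. On the criteria, the SAP says: "The evaluation of overall response will be based on response, as determined by the investigator, in accordance with RECIST version 1.1", for solid tumors, "or IWG 2014 criteria, for subjects with lymphomas". TTR runs to the first documented response, and the DOR set is everyone who responds at any point in the study.

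**Protocol Appendix K (RECIST 1.1, solid tumors).** Three limits apply:

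- Confirmation: "Complete or partial responses may be claimed only if the criteria for each are confirmed by a repeat assessment at least 4 weeks later" (section 3.4, repeated in the introduction and in 4.1).
- End of reading: "The best overall response is the best response recorded from the start of the treatment until disease progression/recurrence" (section 3.4).
- Stable disease: "For stable disease (SD), follow-up measurements must meet the SD criteria at least 5 weeks after study entry" (introduction, repeated in 4.1).

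**Treatment past progression.** SAP 2.1 says: "Subjects receiving clinical benefit may continue on study after a discussion between the Principle Investigator and Medical Monitor". Protocol 5.3 allows the same explicitly when progression is suspected or confirmed. Responses can therefore be recorded after PD.

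**SAP 11** names one change from the protocol, the added duration of clinical benefit endpoint.

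**The concern.** The same scan record can give two different best responses, depending on which document the programmer follows. A PR at the first scan followed by SD is SD in the Appendix K table and PR under the SAP's BOR wording. A patient who progresses, stays on treatment and later has a scan read as PR is PD under Appendix K and PR under the SAP.

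The uncertainty extends past BOR. An unconfirmed responder who is counted in ORR also enters TTR and DOR, and those summaries then describe patients whom the protocol would not call responders. ORR is tabulated by dose cohort, where one patient is a large fraction. The trial is open-label with investigator-assessed response, and Protocol 3.2 says that observations from dose escalation help choose the expansion populations.

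**Working it through.** The documents give no assumed response rate or response count, so there is no planned figure to reproduce. The check sets the two rules against the same scan records.

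**Inputs**

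- First scheduled scan (Protocol 6.10): before Cycle 3 for DR-A and DR-A-2, 2 × 28 = day 56; before Cycle 4 for DR-B, 3 × 21 = day 63.
- SD minimum (Appendix K): 5 × 7 = 35 days.
- Confirmation gap (Appendix K): 4 × 7 = 28 days.
- Interval method (SAP 9): two-sided 95% Wilson score.

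**1. Patterns side by side, on scheduled scans**

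| Recorded sequence | SAP 4.2 BOR, read literally | Appendix K |
|---|---|---|
| PR, SD | PR | SD |
| PR, PD | PR | SD |
| PR, then not evaluable | PR | SD |
| PD, PR | PR | PD |
| Not evaluable only | no category | NE |

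**2. Direction.** I scored every sequence of 1 to 4 assessments drawn from CR, PR, SD, PD and NE, which is 5 + 25 + 125 + 625 = 780 sequences. One scoring took the maximum ever recorded. The other followed Appendix K: the next assessment confirms at 28 days or more, SD needs 35 days, reading stops at first PD, and an unconfirmed CR or PR falls back to SD. The 56-day and 63-day schedules gave the same counts:

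- Responder status (CR/PR) was higher under the maximum-ever rule in 456 sequences and lower in 0. With the stop at PD ignored, 404 remain, so most of the gap comes from confirmation.
- Disease-control status was higher in 168 sequences and lower in 0. With the stop at PD ignored, 0 remain.
- With an assumed unscheduled scan on day 28, 45 disease-control differences remain even with the stop at PD ignored.

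These are counts of possible patterns, not probabilities.

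**3. Why DCR is mostly unaffected.** Days 56 and 63 both lie beyond day 35, so the SD minimum does not bind at a scheduled scan. An unconfirmed CR or PR falls back to SD and still counts as disease control.

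**4. Response after progression.** SAP 4.2 computes DOR as (progression date − first response date + 1)/30. With PD on day 56 and a first PR on day 112:

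(56 − 112 + 1)/30 = −55/30 = −1.8 months.

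**5. Illustrative size** (the response counts are assumed). The Wilson limits are [p + z²/(2n) ± z√(p(1−p)/n + z²/(4n²))] / (1 + z²/n), with z = 1.96 and n = 6:

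- 0/6: lower limit 0; upper limit z²/(n + z²) = 3.84/9.84 = 39%.
- 1/6: (0.487 ± 0.437)/1.640, giving 3% to 56% around 16.7%.

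Pooling dilutes the effect. With an assumed 60 evaluable patients, 4 recorded against 2 confirmed responders is 6.7% (2.6 to 15.9%) against 3.3% (0.9 to 11.4%).

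**The case against.** The strongest reply is that SAP 4.2 does not derive ORR and DCR from BOR. It refers both to investigator response under RECIST 1.1, and in this protocol RECIST 1.1 means Appendix K. On that reading the confirmation rule is already imported, and the silence in SAP 11 means that no departure was intended.

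Part of this stands. A reader might infer that ORR is certain to be overstated, and the documents do not support that: no passage says that ORR is the maximum of the time-point responses. But the reference does not settle the rule. Appendix K 3.4 makes confirmation depend on the nature of the study and ties it to trials where response is primary. The Appendix K introduction says response is not primary here, yet still states confirmation as mandatory. SAP 4.2 does not cite the appendix, and its wording for TTR and DOR fits an ever-responder count. Two programmers could follow the SAP and report different ORRs. The BOR sentence itself conflicts with Appendix K on any reading.

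A second reply is that the DOR definition presumes that response comes before progression, and that a new lesion keeps the overall response at PD whatever the target lesions do. That makes a post-progression PR less common. It does not exclude one, for example after progression by target growth or on clinical grounds.

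Other replies hold and limit the point:

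- A general inflation of DCR might be inferred, but steps 2 and 3 of the working show it does not follow on scheduled scans.
- The conflict does not carry over to lymphoma. Those patients fall under IWG 2014, and the Appendix L table shows no 4-week confirmation or SD minimum.
- A reader might carry the concern to the Phase 2a primary ORR. SAP 3.1 leaves Phase 2a to a separate plan that is not among these documents.

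**Conclusion.** The point holds for solid-tumor patients in Phase 1. The BOR definition conflicts with Appendix K on confirmation and on the stop at progression, and the departure is undeclared. Read literally, BOR can be overstated and never understated. For ORR, and for the responder set behind TTR and DOR, the finding is an open rule whose literal reading errs upward; an actual overstatement is not shown. DCR is touched only by assessments after progression or by unscheduled scans before week 5. A first response recorded after progression would give a negative DOR, so a rule is needed whatever view is taken on confirmation.

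The size cannot be derived from the documents. The shift from 0/6 to 1/6 illustrates one assumed unconfirmed PR. The intervals overlap widely, and no decision threshold is attached to them.

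One further assumption: SAP 11 rests on protocol Amendment 6, while the protocol supplied contains Amendment 7 material. I take Appendix K to be the same in both.

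Severity is moderate. Clinical activity is a secondary objective in Phase 1 and the analysis is descriptive.

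**What to change.** In SAP 4.2, for solid-tumor patients:

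- Derive BOR from the Appendix K table that applies when CR and PR must be confirmed, and add an NE category here and in SAP 9.
- Count ORR on confirmed CR or PR only.
- Apply the 5-week minimum to SD.
- Use only assessments up to and including first objective progression.
- Date TTR and DOR from the first scan of a confirmed response.
- List unconfirmed and post-progression responses separately, labelled as such.

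State the IWG 2014 rule for lymphoma patients in its own sentence. If the sponsor does intend to count unconfirmed responses, SAP 11 should say so.

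The cost is SAP wording and programming. The next scheduled scan, 8 or 9 weeks later in the first year, can usually serve as confirmation. It will not always exist: Protocol 6.10 waives end-of-treatment imaging when a scan was done in the prior 6 to 8 weeks, and Protocol 6.13 ends Phase 1 follow-up at that visit. A responder who stops before a second scan will therefore count as unconfirmed, and the reported ORR may be slightly lower. The separate listing keeps such patients visible.
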